#### **9.4.4. Use of Imaging Guidance**

Injection by image guidance is at the discretion of the Investigator. Use of image guidance will be recorded in the CRF.

#### **9.4.5. Arthrocentesis**

The presence of clinically-apparent tense effusion in the study shoulder will exclude the subject from inclusion in the study. If effusion is found in the shoulder upon needle placement in the joint space, it must be removed (arthrocentesis) before study/reference product is injected.

Strict aseptic technique must be followed. The same needle will be used for arthrocentesis and the IA injection. Needles from 18 to 22G will be supplied by each study site and the study personnel will choose an appropriate needle.

Gentle aspiration will be performed prior to injection of the study treatment for each subject in an attempt to ascertain that the needle has been placed within the joint space. Any joint fluid will be withdrawn using an empty 20mL syringe (supplied by each study site) and the volume of the aspirated fluid will be recorded in the CRF.

Leaving the needle in the joint space, the aspiration syringe will be removed and replaced by the pre-filled 3mL syringe containing DUROLANE. Care must be taken when exchanging syringes to avoid displacement of the needle and to ensure the syringe with Investigational Product is securely attached prior to injection.

#### **9.4.6. Post-Injection Care**

To monitor for possible injection procedure-related events, subjects should remain at the study site for 30 minutes following injection.

The subjects should be encouraged to rest the injected joint as much as possible for at least 24 hours. Subjects are allowed to return to work, but strenuous activities and driving long distances should be avoided the first 48 hours after injection.

Subjects should be informed that there could be pain associated with the injection procedure. For post-injection pain management, subjects should rest and apply ice at the injection site for 20-minute intervals, if needed. In the event of persistent pain, the subject may take recommended rescue medication (see Section 10). All pharmacological and non-pharmacological treatments of post-injection pain must be captured in the CRF.

#### **9.4.7. Documentation of Treatment Procedure**

All procedures will be carefully documented in the medical notes and in the CRF. The subject number, date and time of injection, study shoulder, needle size, possible use of topical, subcutaneous and intra-articular anesthetics, arthrocentesis volume, volume of Investigational Product (3mL) injected and possible technical or medical problems with the injection will be recorded in the CRF by the Investigator.

After the injection, the syringe and packages should be discarded according to approved institutional disposal policy. An Investigational Product Dispensing Log is to be maintained by the site.

#### **9.4.8. Reporting Technical Complaints**

All technical complaints regarding the Investigational Product are to be reported to the Sponsor promptly.

AEs and other clinical findings prior, during or immediately post-injection must be recorded. Subjects experiencing pain and swelling at the study shoulder or any other AEs will be instructed to contact the study staff.

### **9.5. Investigational Product Accountability**

The product will be released to each Investigator (or pharmacy located at the study site) after approvals of the protocol have been received from the REB and the Clinical Trial Agreement (CTA) has been finalized and signed by the study site.

The Investigator must ensure that the Investigational Product is kept under secure conditions, with access limited to those authorized by the Investigator per the Delegation of Authorities Log.

The Investigational Products must be traceable from the manufacturer to their use in subjects and the Investigator must maintain accurate product accountability records, i.e., documentation of deliveries and return of Investigational Product between the Sponsor or their representative and the Investigator, and documentation of administration of product to the subject.

A log will be kept of all Investigational Product received from the Sponsor. In addition, dispensing logs will be maintained including the date, amount dispensed, and the

subject receiving Investigational Product. Logs for all accountability procedures are provided by the Sponsor.

When the study is completed, all unused investigational product at each study site must be returned to the Sponsor for destruction, with proper documentation, unless otherwise instructed by the Sponsor.

Products deliberately or accidentally destroyed during shipment or at a study site should be accounted for and documented. Used syringes should be destroyed according to the procedures at the clinic. Disposal of hazardous material, i.e., syringes and needles, must conform to applicable laws and regulations. The Investigational Product must not be used outside the study.

## **10. CONCOMITANT MEDICATIONS /TREATMENTS**

Except as noted below, concomitant medications or other treatments or procedures may be given at the discretion of the Investigator when medically necessary. All concomitant therapy used during the study, should be recorded in the CRFs, by the name (generic name for pharmacological therapy), start and end date, and indication.

The restrictions on treatments and the specified time periods prior to and during the study are provided in the inclusion/exclusion criteria. Except for analgesic given for management of persistent post-injection pain and for short-term relief of pain other than shoulder pain, the Investigator should contact the Sponsor prior to implementation of these therapies. All such therapy used during the study is to be recorded in the CRF.

For rescue medication, subjects will be instructed to take as needed of acetaminophen not to exceed 4g/day. Subjects will be required to purchase this for themselves as needed. A shoulder pain rescue medication diary will be provided to the subject at the screening visit to record intake of rescue medication. The diary will be reviewed at baseline, Week 6, Week 12, Week 18 (via phone) and Week 26. Any use of rescue medication since last visit will be recorded in the CRF.

Acetaminophen is also the preferred analgesic for other types of body pains while the subject is in the study. Usage will be documented in the subject's shoulder pain rescue medication diary and Concomitant Medications CRF page.

Any concomitant medications, including over-the-counter (OTC) medications, administered during the study are also to be recorded in the CRF and in the shoulder pain rescue medication diary.

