### **5.3. Potential Risks and Benefits**

#### **5.3.1. Potential Risks**

##### **5.3.1.1. Risks Associated with the Use of DUROLANE**

There is a lack of published data related to the use of viscosupplementation for joints other than the hip and knee (e.g. ankle, shoulder, temporal mandibular joint, etc.). The majority of the reported adverse reactions in DUROLANE clinical studies of the knee and hip were described as transient pain, swelling and/or stiffness locally in the joint. It is unclear if these adverse reactions were related to the injection procedure or DUROLANE. These adverse reactions were mild or moderate in intensity and only occasionally required treatment with analgesics. A review of the literature related to the use of other HA preparations in other joints did not reveal any additional unique AEs (Durolane IFU, 2012). The type of adverse reactions associated with the use of DUROLANE in shoulder are likely to be the same as those observed in hip and knee.

The differences in physical and chemical properties between DUROLANE and other HA preparations have been assessed not to influence the safety and tolerability when injected intra-articularly (Q-Med, 2012). The risks associated with the IA injection will be minimized by only allowing clinicians to participate who have adequate education and are experienced in the delivery of IA shoulder therapies.

As with any treatment, unexpected reactions may occur. The study contains an exclusion criterion for those subjects with a previous history of an allergic response to a HA-based product. However, should a reaction occur, the subjects will be informed to contact the study site immediately and be given immediate advice about any necessary medical treatment.

Many subjects with shoulder pain receive treatment with anti-inflammatory drugs. Subjects who decide to take part and are receiving anti-inflammatory drugs must stop such treatment for a time sufficient for the given medication to clear the body (at least 5 half-lives of drug activity) before the shoulder injection is made and refrain from using such medications during the rest of the study period. This may increase the risk that study subjects experience shoulder or other bodily pain. However, to mitigate such risk, all subjects will be allowed to take rescue medication (acetaminophen) during the study for such pain. Other analgesics are prohibited.

All subject use of rescue medication will be recorded in the CRF.

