**Table 2: Schedule of Events**

Activities	Visit 1 (screening)	Visit 2 (baseline)	Visit 3	Visit 4	Visit 5 (telephone contact)	Visit 6 (final study visit)
	Week -1 to -2 (≤ 14 days)	Week 0 (Day 0)	Week 6 (±7 days)	Week 12 (±7 days)	Week 18 (±7 days)	Week 26 (±7 days)
Informed consent	X					
Review of inclusion/exclusion criteria	X	X				
Demographics	X					
Medical history, including shoulder OA	X					
X-ray of the study shoulder	X 					
Review of concomitant medications/therapies	X	X	X	X	X	X
Physical examination including height and weight, vital signs	X	X	2	2		X
Physical examination of the study shoulder (SS)	X	X	X	X		X
Physical examination of the contralateral shoulder	X	X				
Washout of analgesics	X 	X 	X 	X 	X 	X 
Urine pregnancy test		X 				
VAS Shoulder pain on movement – contralateral shoulder	X	X				
VAS Shoulder pain on movement – SS	X	X	X	X	X 	X
VAS Shoulder pain at night – SS		X	X	X	X 	X
VAS Patient global assessment		X	X	X	X 	X
ASES Patient self-evaluation (VAS pain today and ADL only) – SS		X	X	X	X 	X
ASES Physician assessment range of motion only – SS		X	X	X		X
Dispense Week 18 VAS pain, PGA, and ASES patient self-evaluation forms				X		
Intra-articular shoulder injection		X				
Instruct subject on rescue medication use	X	X	X	X	X	
Dispense shoulder pain rescue medication diary	X					
Review shoulder pain rescue medication diary and record intake on CRF		X	X	X	X	X
Review and report adverse events (AEs)		X	X	X	X	X
Collect shoulder pain rescue medication diary						X

1. If a radiograph was not taken within 6 months of the screening visit, then a radiograph must be taken as standing x-rays in the anterior-posterior and lateral plane views. Radiographs must be read by a local radiologist or the orthopaedic surgeon.
2. As clinically indicated.
3. At least 5 half-lives of current analgesic must have passed before Baseline Visit to confirm eligibility.
4. No acetaminophen is to be taken for 24 hours before each study visit (Weeks 0, 6, 12, 18, 26). No other analgesic is to be taken during the course of the study.
5. Urine pregnancy test will be performed on all females of childbearing potential.  
At the Week 12 visit VAS pain, PGA, and ASES patient self-evaluation forms will be dispensed to the subject to be completed at the time of the Week 18 telephone contact.

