### 8.1. Subject Inclusion Criteria

1. Females or males between the ages of 19 and 85 years of age
2. Diagnosis of glenohumeral osteoarthritis (GH-OA), confirmed by radiographs taken within the previous six months, with GH-OA being the primary source of pain; OA in the contralateral shoulder is permissible provided that OA symptoms are greater in the trial shoulder
3. Shoulder pain on movement (SPOM) visual analogue scale (VAS) (0-100mm)  $\geq 50$ mm for the study shoulder
4. Must be willing to discontinue use of oral and topical analgesia other than rescue use of acetaminophen for the study shoulder. Must also be willing to discontinue rescue medication for at least 24 hours before each visit
5. Abstinence from any IA or peri-articular injections for the shoulder during the course of the trial, except for the assigned Investigational Product
6. Patients with chronic shoulder pain lasting more than 6 months without clinically significant improvement in shoulder pain over the past one month
7. Pain at least 50% of the days during the previous month
8. Patients who have failed conventional therapy including but not limited to the following: nonsteroidal anti-inflammatory drugs (NSAIDs); one or more intra-articular or local peri-articular steroid injections and physiotherapy (a minimum of one month of previous physiotherapy treatment is required)
9. Patients with a retained active range of motion (ROM) of at least 30% in all directions to rule out frozen shoulder ( $>30^\circ$  for abduction with scapula fixed,  $>30^\circ$  for external rotation, and  $>20^\circ$  for internal rotation)
10. Cooperative and able to communicate effectively with the Investigators
11. Must agree not to participate in any other clinical research (interventional) studies while participating in this study
12. Body mass index (BMI)  $\leq 35$  kg/m^2
13. English literacy and ability to understand and complete all informed consent procedures

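### The 24-hour analgesic washout applies at all five assessments but a breach forces rescheduling only at baseline, and Section 10's wording loosens the ban on other analgesics (low severity, cheap to fix)

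*Protocol*

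**What the plan says.** **Which analgesics are allowed.** Section 10 requires Sponsor contact before restricted therapies are given, with the carve-out "Except for analgesic given for management of persistent post-injection pain and for short-term relief of pain other than shoulder pain". It adds: "Acetaminophen is also the preferred analgesic for other types of body pains while the subject is in the study". For the restrictions themselves it points elsewhere: "The restrictions on treatments and the specified time periods prior to and during the study are provided in the inclusion/exclusion criteria".

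Seven other places ban every analgesic except acetaminophen: Section 5.3.1.1, Table 2 footnote 4, Sections 7.4.1, 7.4.2, 7.4.3 and 8.5.1, and Appendix 2. Section 5.3.1.1 says of stopping anti-inflammatory drugs: "This may increase the risk that study subjects experience shoulder or other bodily pain". It offers acetaminophen for such pain and then says "Other analgesics are prohibited". Footnote 4 of Table 2 says "No other analgesic is to be taken during the course of the study".

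**When analgesics must be stopped.** The same footnote sets the washout at every assessment: "No acetaminophen is to be taken for 24 hours before each study visit (Weeks 0, 6, 12, 18, 26". Sections 7.4.1 and 11.3 extend the 24-hour rule to any analgesic.

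**What happens on a breach.** At baseline (7.4.2) the subject is asked about the previous 24 hours. Acetaminophen in that window makes rescheduling mandatory, and another analgesic not cleared for five half-lives also leads to rescheduling. At Weeks 6, 12 and 18 (7.4.3) the diary is reviewed, use since the last visit is recorded, and counselling is given. At Week 26 (7.4.4) the diary is reviewed and use recorded, with no action stated.

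**The concern.** The primary test compares the mean of four follow-up shoulder-pain-on-movement (SPOM) scores with baseline in one group of patients. SPOM asks about the last 24 hours (Section 12.1), the same window as the washout. An analgesic active in that window can lower the score.

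At baseline the plan prevents this by moving the visit. At follow-up it forbids the dose but gives no instruction to move the assessment when the rule is broken, so the medicated score enters the contrast. With no control arm nothing offsets the effect, and it acts towards success.

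The Section 10 wording adds a smaller problem. An investigator who relies on that section could allow an NSAID for, say, a back strain in good faith, while Appendix 2 prohibits it.

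**Working it through.** **Step 1. Does Section 10 conflict with the ban?**

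- The carve-out waives Sponsor contact; it does not name or grant a drug.
- Two features imply a choice of drug. Acetaminophen is already permitted (Appendix 1), so a waiver covering it alone would do little. Calling it preferred also presupposes alternatives.
- The pointer to the eligibility criteria does not clearly settle the matter. Inclusion 4 reads "Must be willing to discontinue use of oral and topical analgesia other than rescue use of acetaminophen for the study shoulder", and its last words can be attached either to all analgesia or only to the rescue use. Exclusions 6 and 8 concern the time before baseline. Exclusion 21 covers only aspirin.
- For post-injection pain there is no conflict, because Section 9.4.6 directs the subject to rescue medication. The conflict is limited to non-shoulder pain.

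**Step 2. What does that wording open?** Sections 7.4.1 and 11.3 bar any analgesic within 24 hours of a visit. A subject following Section 10 on its looser reading could therefore take a longer-acting drug, for example, two days before a follow-up visit and still meet the 24-hour rule. Baseline asks for more: five half-lives in 7.4.2, and one week or five half-lives, whichever is longer, in exclusion 6. The wording by itself opens that carry-over and nothing inside the 24-hour window.

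**Step 3. Rule and consequence, assessment by assessment.**

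| Week | 24-hour washout | Action stated if broken |
|---|---|---|
| 0 | yes | reschedule (7.4.2) |
| 6, 12, 18 | yes | counselling (7.4.3) |
| 26 | yes | none (7.4.4) |

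A rescheduling rule exists at one of five assessments. The specific question about the previous 24 hours is also written only for baseline.

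**Step 4. Scale.** Section 14.2 gives SD 25 mm, correlation 0.5 and n = 29. Its sample size reproduces:

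- Means 60, 55, 50, 45 average 52.5, so V = (56.25 + 6.25 + 6.25 + 56.25)/4 = 31.25.
- Effect size = 31.25/(625 × 0.5) = 0.10; noncentrality = 4 × 29 × 0.10 = 11.6 on 3 and 84 degrees of freedom.
- Power is 0.807 at n = 29 and 0.791 at n = 28.

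For the contrast (mean of four follow-up visits minus baseline), with the same inputs and complete data:

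- Variance per subject = 625 × [(1 + 3 × 0.5)/4 + 1 − 2 × 0.5] = 625 × 0.625 = 390.6.
- Standard error = √(390.6/29) = 3.67 mm.

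Shift in the contrast = share of follow-up scores affected × reduction per affected score. Both inputs are assumptions; the protocol gives neither.

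| Share | Reduction | Shift | In standard errors |
|---|---|---|---|
| 5% | 5 mm | 0.25 mm | 0.07 |
| 10% | 10 mm | 1.0 mm | 0.27 |
| 20% | 20 mm | 4.0 mm | 1.09 |

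With no true change, a 1 mm shift raises the chance of declaring success from 0.05 to 0.084 for a one-sided 0.05 test, or from 0.025 to 0.045 in the favourable direction for a two-sided one (noncentral t, 28 degrees of freedom). At 4 mm the figures are 0.281 and 0.182.

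For comparison, the planned follow-up means average (55 + 50 + 45)/3 = 50 mm, a 10 mm fall from 60. The assumed shifts are 2.5% to 40% of that, and 10% in the middle case.

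**The case against.** **Section 10 can be read in line with the ban.** Acetaminophen is itself restricted in timing, so the carve-out could mean that drug alone. Section 5.3.1.1 answers the non-shoulder case directly, and Section 7.1 describes stopping oral analgesia other than acetaminophen with no shoulder limit. Much of this stands: the wording implies a permission and does not grant one. It still leaves a site with two instructions that do not match.

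**The stronger inference fails.** A reader might infer that Section 10 lets subjects take other analgesics in the 24 hours that SPOM covers. Sections 7.4.1 and 11.3 exclude that. Bias inside the window needs a washout breach, whichever way Section 10 is read.

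**Baseline differs for a reason.** Rescheduling there enforces eligibility (exclusion 8), and no eligibility decision is made later. At follow-up the washout is still scheduled, discussed with the subject and backed by diary review. This explains the difference but does not remove its effect on the comparison.

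**Analysis of breached scores may belong in the SAP.** It may, and its absence here is no finding. But moving an assessment is a conduct rule, and later analysis can flag or exclude a medicated score without recovering an unmedicated one.

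**The millimetre figures are assumed.** This stands in full. The ban is repeated to subjects, and exclusion 1 removes those needing chronic analgesia for other pain, so the low end of the range is the more likely.

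**Conclusion.** The point holds at low severity, as a cheap improvement. Its main part is the missing follow-up rule: under the plan as written, a SPOM score taken after a washout breach is kept and set against a baseline that had to be clean. The direction favours success. The Section 10 wording is a lesser inconsistency whose only route of its own to the endpoint is carry-over from longer-acting drugs.

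The size cannot be derived from the protocol. The illustration of 0.25 to 4 mm (0.07 to 1.09 standard errors) rests on assumed shares and effects, and on the planning SD, correlation and n = 29 with complete data. A reader might infer that the primary result would be materially inflated or the trial invalid; nothing in the protocol supports that, since it gives no breach rate and no analgesic effect on SPOM.

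**What to change.** - **Section 10:** limit the carve-out to acetaminophen, and make acetaminophen the only permitted analgesic for other body pains in place of the preferred one.
- **Sections 7.4.3 and 7.4.4:** ask about analgesic use before SPOM is marked (at Week 18, before the forms are completed at home). If acetaminophen was taken in the previous 24 hours, or another analgesic within five half-lives (the 7.4.2 standard), reschedule within the existing ±7-day window. If that is not possible, complete SPOM anyway and record a protocol deviation.

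The five-half-life trigger is needed because a 24-hour question alone would miss longer-acting drugs taken in breach of the ban. The cost is two wording edits, a short addition to each of the two visit sections, and a few rescheduled visits or calls. No assessment is lost, because SPOM is still collected when rescheduling fails.

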#### **6.1.2. Secondary Objectives**

To evaluate the efficacy of a single IA injection of DUROLANE 3mL given for treatment of symptomatic OA of the shoulder followed over a 26-week time period for:

- shoulder pain at night
- shoulder range of motion
- shoulder pain rescue medication use

To evaluate the safety and tolerability of a single IA injection of DUROLANE 3mL over a 26-week time period

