#### 7.4.1. Screening Visit

The prospective subject must be informed about the study both orally and in writing, and the ICF must be signed prior to initiation of any study related procedure. Inclusion into this study requires literacy in English sufficient to complete the informed consent process and ability to complete effectiveness assessment forms. A study number will be assigned chronologically to each subject screened per the Screening and Enrollment log. Based on a chart review and discussion with the subject, the following demographic data will be recorded in the CRF: anonymized subject initials, gender, date of birth, ethnic origin, weight, and height. Medical history, including OA history and concurrent diseases will be queried and recorded on the CRF. The assessments of OA history at the screening visit will consist of: duration of diagnosed shoulder OA (i.e., time since

diagnosis), duration of persistent shoulder pain, OA in joints other than the shoulder, clinically-significant pain from other parts of the body than the shoulder, and history of prior medications and interventions for shoulder OA (including IA injections, surgical procedures, and any traumatic injury). Concomitant medications and non-pharmacological treatment of shoulder OA will be recorded in CRF logs.

A full physical examination including vital signs, height and weight will be conducted. Physical examination of both shoulders will be performed. Evidence of joint inflammation, as reflected by clinically-tense effusion and tenderness on palpation will exclude the subject from the study.

Radiographs of the study shoulder will be performed, if a radiograph taken within six months of the screening visit does not exist. Assessment of radiographs will be made by either the Study Investigator or the local radiologist. The SPOM VAS (0-100mm) assessment will be completed for both shoulders. A pain score  $\geq 50$ mm is required for the study shoulder and must be  $\leq 20$ mm for the contralateral shoulder to be eligible.

For eligibility, symptomatic OA of the contralateral shoulder should be responsive to acetaminophen and not require any protocol prohibited therapies that would confound measurement of pain in the study shoulder. Also, low back pain requiring chronic ongoing analgesic therapy is an exclusion criterion.

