### **11.3. Concomitant Medications (All Visits)**

Any therapies for other diseases that are considered necessary for the subject's welfare may be given at the discretion of the Investigator. All concomitant therapy used during the study, should be recorded in the CRFs by the name (generic name for pharmacological therapy), the start and end date, and indication.

Acetylsalicylic acid up to 325mg per day is allowed during the study as thrombosis prophylaxis. Acetylsalicylic acid for analgesic purposes is not allowed. The prohibition for taking any analgesic 24 hours before a visit also applies.

No other product under investigation may be used concomitantly with the Investigational Product.

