#### **12.5. Recorded Use of Rescue Medication**

Subjects will be advised to take acetaminophen as rescue medication for study shoulder pain as required. Acetaminophen intake will be recorded in the shoulder pain rescue medication diary which will be transcribed on the CRF.

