**14.1.3.5. Secondary variables**

The weeks 0, 6, 12, 18 and 26:

- VAS (0-100mm) SPAN
- ASES patient self-evaluation (PSE) Shoulder Score Index (SSI): (range: 0-100)
- VAS (0-100mm) PGA

- Shoulder pain rescue medication consumed (unit: average mg per week)

The weeks 0, 6, 12, and 26:

- ASES physician assessment (PA) range of motion (ROM): 5 questions (active and passive; total 10 assessments) (unit: degrees)

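### Acetaminophen for other body pains goes into the shoulder rescue diary, and the protocol does not ensure its milligrams can be separated from the shoulder rescue endpoint

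*Protocol*

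**What the plan says.** Section 6.1.2 names "shoulder pain rescue medication use" among the secondary efficacy objectives. Section 14.1.3.5 sets the variable as "Shoulder pain rescue medication consumed (unit: average mg per week"), reported for weeks 0, 6, 12, 18 and 26.

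The sections that feed this variable are:

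- **Section 12.5:** "Subjects will be advised to take acetaminophen as rescue medication for study shoulder pain as required". It then says that acetaminophen intake is written in the diary and transcribed to the CRF. The Schedule of Events (Table 2) likewise has staff review the diary and record intake.
- **Section 10:** "Acetaminophen is also the preferred analgesic for other types of body pains while the subject is in the study". That use is to be documented in the "shoulder pain rescue medication diary and Concomitant Medications CRF page".
- **Section 5.3.1.1:** on the withdrawal of anti-inflammatory drugs, "This may increase the risk that study subjects experience shoulder or other bodily pain". Rescue acetaminophen is then allowed for pain of that kind.
- **Section 11.3, with the same list in Section 10:** concomitant therapy is to be "recorded in the CRFs by the name (generic name for pharmacological therapy), the start and end date, and indication". Dose is not in the list.
- **Section 7.4.1:** for eligibility, "symptomatic OA of the contralateral shoulder should be responsive to acetaminophen". The contralateral shoulder must also score no more than 20 mm on movement.

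**The concern.** The endpoint is specific to one shoulder and is measured in milligrams. The diary that supplies it also receives acetaminophen taken for other pains. Unless each entry carries a reason, the milligrams taken for the study shoulder cannot be told from the rest. The concomitant-medication page would show that other use occurred and when, but its listed fields would not show how much.

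Some non-shoulder use is foreseeable. Other analgesics are prohibited during the study (Section 5.3.1.1, Appendix 2), and contralateral osteoarthritis that responds to acetaminophen is admitted. Section 8.5.1 itself notes that rising acetaminophen use may reflect either the study condition or a different pre-existing disease.

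At stake is the reading of one named secondary objective. The trial is single-arm, so no control group exists in which non-shoulder use could balance out. Steady use elsewhere would shrink the percentage fall in recorded intake. A change in pain elsewhere could look like a change in shoulder rescue use.

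**Working it through.** The protocol gives no figure to reproduce, so the check follows the data from intake to endpoint.

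**1. What counts as rescue use.** Section 12.5 ties it to study-shoulder pain. Section 5.3.1.1 extends it to shoulder or other bodily pain. Section 9.4.6 also treats acetaminophen for persistent post-injection pain as rescue medication. The scope differs between sections.

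**2. What enters the diary.** Under Section 10, acetaminophen for other body pains is entered, and so are all other concomitant medications. The diary is therefore broader than the endpoint.

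**3. What leaves the diary.** Section 12.5 and Table 2 transcribe intake to the CRF. Neither states a restriction by reason.

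**4. What the second record adds.** Non-shoulder use is also recorded on the concomitant-medication page. The listed fields are name, dates and indication. These can flag an affected period but supply no milligrams to subtract.

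**5. What the variable needs.** Average mg per week for the shoulder needs an amount and a reason for each intake. The unit implies that the diary holds amounts. No section requires a reason in the diary.

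**Scale, on assumed figures only.** The documents give no amount of non-shoulder use. Let S be weekly study-shoulder use and O weekly use for other pain, and suppose both were summed.

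- Level: if a share s of the total is for other pain, the shoulder figure is overstated by a factor of 1/(1 − s). That is 1/0.90 = 1.11 at s = 10%, 1/0.75 = 1.33 at 25%, and 1/0.50 = 2.00 at 50%.
- Percentage fall: with O constant, recorded fall = (S before − S after)/(S before + O). Take S falling from 6,000 to 3,000 mg/week, a true fall of 50%.
  - O = 3,000: 3,000/9,000 = 33%.
  - O = 6,000: 3,000/12,000 = 25%.
- Absolute fall: with O constant it stays at 3,000 mg/week in both cases (9,000 − 6,000 and 12,000 − 9,000). If O changes, its change adds directly to the recorded change.

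**The case against.** A reader might infer that the endpoint counts acetaminophen taken for any pain. The protocol does not say so. The variable is named for shoulder pain, and the first sentence of Section 12.5 limits rescue use to the study shoulder. Because the diary also holds every other concomitant medication, being written there does not by itself mean being counted. Sections 7.4.1, 7.4.2 and 7.4.3 mention rescue and other concomitant medication as separate kinds of entry.

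A reader might also infer that non-shoulder use could never be removed. That is not shown either. The diary and CRF layouts are not in the document, the field lists do not exclude a dose, staff review the diary at each contact, and the double recording with indication and dates identifies affected periods.

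Two further objections concern size. Exclusion 1 removes significant pain elsewhere that needs chronic analgesic therapy, and the contralateral shoulder may score at most 20 mm. The milligram figures above are assumptions. Under Section 14.1.1 the secondary variables have no planned test, so any inference from this one is exploratory.

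These objections stand and narrow the point. It could also be said that turning diary entries into mg per week belongs in the statistical analysis plan. That is right for the derivation rule but does not answer the gap in data capture, because an analysis plan cannot recover a reason for intake that was never collected.

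**Conclusion.** The point holds in limited form. The protocol routes non-shoulder acetaminophen into the shoulder diary, passes diary intake to the CRF without limiting it by reason, and lists no dose for the record that carries the indication. It is also inconsistent on the pains that rescue medication covers. As written, it does not ensure that the shoulder-specific variable can be separated at the level of milligrams.

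The amount of any contamination is unknown, and the eligibility limits restrain it. One secondary, descriptive variable is affected. The primary pain-on-movement test and the success criterion are not. The conclusion assumes that the diary, whose layout is not shown, has no reason field. If it has one, what remains is the inconsistent scope in the text. This is a cheap improvement.

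**What to change.** 1. Reconcile Sections 5.3.1.1, 10 and 12.5 on what is recorded as shoulder rescue use.
2. On the diary and the CRF, record for each acetaminophen intake the amount in mg and the reason, in two categories: study shoulder, including post-injection shoulder pain, or other pain. A separate post-injection category left out of the endpoint would drop intake that Section 9.4.6 treats as rescue medication.
3. Define the variable in Section 14.1.3.5, and in the matching synopsis entry, as mg per week taken for the study shoulder. Report total acetaminophen per week as a supporting summary.

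The cost is one extra diary and CRF column and a slight burden on subjects. What subjects may take does not change. The change needs to be in place before diaries are issued, because reasons are hard to recover afterwards.
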